### 4.3. Secondary Endpoint(s) Analyses (Part A)

Prior to the final study analysis, all secondary endpoint analyses will be based on the ES (e.g. interim analysis, analyses to support IDMC and iDRC). At the final analyses immunogenicity will be based presented for both ES and PPS.

For each variant CCI [REDACTED], a secondary comparison of the immunogenicity of CV0701 and CV0601 booster vaccines with CCI [REDACTED] vaccine will be performed as follows:

[figure not shown]
- Serum neutralization at Day 91 and Day 181 (GMT)
- Seroresponse from baseline of serum neutralization titers at Day 29 (percentage of participants)
- Fold increase from baseline of serum neutralization titers at Day 29, Day 91, and Day 181 (GMI)

#### 4.3.1. Main analytical approach

The analyses of secondary endpoints at the specified time points will be performed as described in Section 4.2.2.

### 4.4. Tertiary/Exploratory Endpoint(s) Analyses (Part A)

[figure not shown]
CCI [REDACTED]

[figure not shown]
**CONFIDENTIAL**

219075

CCI

CCI

## **4.5. Safety Analyses**

Refer to Section 4.2.1.

#### **4.5.1. Independent Data Monitoring Committee (IDMC) and Safety Review Team (SRT) and Internal Data Review Committee (iDRC)**

An unblinded IDMC will review all available safety (and/or immunogenicity) data at scheduled timepoints. The IDMC will meet at the following timepoints:

- After 20% of participants have completed solicited reporting period (Day 7).
- Interim analysis, which will be based on Day 29 data from all participants.
- Every 3 months until the end of the study.
- Ad hoc meetings, as needed, to review safety data.

The SRT will contribute to the continual assessment of incoming new safety (and efficacy) information. The SRT will remain blinded to study group allocation.

An unblinded iDRC will review safety, reactogenicity, and immunogenicity data from the Day 29 interim analysis to make recommendations on dose selection for a future Phase 3 study.

The Tables Figures and Listings to be generated to support IDMC and SRT reviews will be detailed in a dedicated output programming specification (OPS).

#### **4.6. Other Analyses**

A table summarizing solicited as well as unsolicited AEs excluding SAE will be provided by group – the number and percentage of participants with AE will be provided with exact 95% CI. Unsolicited AEs will also be tabulated by MedDRA PT and SOC.

##### **4.6.1. Subgroup analyses**

For primary immunogenicity and seroresponse endpoints subgroup analysis will be performed by age (< 65 years, ≥ 65 years), prior infection, number of prior COVID-19 vaccinations and country if there are at least 15 participants with data per vaccine group in each subgroup. For immunogenicity endpoints subgroup analysis will focus on between group summaries only based on the PPS.

#### **4.7. Interim Analyses**

For each study part, an interim analysis will be performed based on safety and immunogenicity data (neutralization titers matched to the variant encoded on the study vaccines) for all participants up to Day 29. To maintain the study blinding, the unblinded analysis will be available to the IDMC, iDRC core members and study statisticians in charge of the analysis. In addition, aggregate summaries will be used for regulatory interaction before LSLV. However, all efforts will be made to ensure that participants, investigators and monitoring staff will continue to remain blinded. Sequence of interim and other planned analyses is as follows:

- Interim analysis: up to Day 29 safety and immunogenicity data (neutralization titers matched to the variant encoded on the candidate vaccines) for all participants (Part A and B separately).

- Final analysis: up to Day 181 safety and immunogenicity data for all participants (Part A and B separately).

The interim analysis as well as safety and immunogenicity analyses to support IDMC, iDRC and SRT will be based on the ES.

#### 4.8. Changes to Protocol Defined Analyses

There were no changes or deviations to the originally planned statistical analysis specified in the protocol amendment 1 (Dated: 26 September 2023).

### 5. SAMPLE SIZE DETERMINATION

#### Part A

Approximately 415 participants will be enrolled in the study and randomized in a 1:1:1:1:1 ratio to receive 1 of the 3 CV0701 formulations, CV0601, or the comparator vaccine (i.e., 83 participants will be enrolled in each of the 5 groups).

Part A will provide preliminary evidence of CCI

CCI  
CCI  
CCI  
CCI  
CCI  
CCI  
CCI

#### Part B

In Part B, a total of 249 participants will be enrolled and randomized in a 1:1:1 ratio to receive an injection of 1 of the 3 vaccine storage conditions; baseline-control, intermediate or maximum storage conditions (83 participants in each of the 3 groups).

Part B study will provide preliminary evidence of CCI

CCI  
CCI  
CCI  
CCI  
CCI  
CCI  
CCI  
CCI

## 6. SUPPORTING DOCUMENTATION

### 6.1. Appendix 1: Study Population Analyses

Unless otherwise specified, the study population analyses will be based on the exposed set.

#### 6.1.1. Participant Disposition

A summary of the number and percentage of participants who completed the study as well as those who prematurely withdrew from the study will be provided. Reasons for exclusion from analysis will be summarized for the enrolled set and ES.

#### 6.1.2. Demographic and Baseline Characteristics

The demographic characteristics including age, sex, ethnicity, height/weight, body mass index (BMI) ( $\text{kg}/\text{m}^2$ ) on Day 1, race, country, N-protein status, prior COVID-19 infection status (defined by self-reporting or positive N protein at pre-vaccination) and number of prior COVID-19 vaccinations will be summarized with descriptive statistics (see Section 4.1.1). In addition, the following age categories will be summarized: 18-64 and 65-84 based on the Enrolled Set, ES and PPS at day 29.

#### 6.1.3. Protocol Deviations

Important protocol deviations are a subset of protocol deviations (PDs) that may significantly impact the completeness, accuracy, or reliability of the study data or that may significantly affect a participant's rights, safety, or well-being. Important PD rules will be developed and finalized before database lock.

Protocol deviations will be tracked by the study team throughout the conduct of the study. Important PDs include, but are not limited to, the following:

All participant data is excluded from the PPS:

- Study intervention not administered at all
- Invalid/missing informed consent
- Fraudulent data
- Participants got dosed but not as per protocol
- Study intervention storage temperature deviation which is not accepted by quality
- Expired study intervention administered
- Ineligible participant
- no pre-dose and Day 29 anti-neutralizing titer against either the CCI  
CCI

Participant data collected on the day or after the event is excluded from the PPS:

- SARS-CoV-2 infection
- Administration of concomitant vaccine(s) forbidden in the protocol
- Administration of any medication forbidden by the protocol, namely administration during the study period of investigational or non-registered product (drug, vaccine or invasive medical device) other than the study intervention, of long-acting immune-modifying drugs or of immunoglobulins and/or any blood products or plasma derivatives with the exception of monoclonal antibodies specifically directed against the spike protein of SARS-CoV-2 virus, for treatment of COVID-19 disease

Participant lab data collected on the day of the event is excluded from the PPS:

- Participants did not comply with blood sample schedule (see schedule of activities in protocol, Section 1.3)
- Immunogenicity results not available post-dose
- Serological results available but results unreliable (e.g., wrong blood sample management)

The following exclusion codes (as per PPD processes) will be used in this study:

Code	Description
3	Exclude from the PPS only
6	Exclude from the PPS at this visit
7	Exclude from the PPS from this visit onwards
99	Include in all analysis (minor PD)

Note regarding scheduled visits for neutralization samples (D1 D29 D91 D181): For out of window neutralization samples code 6 will be used for all scheduled visits. For missing neutralization samples code 3 will be used for D1 or D29 visits and code 6 will be used for D91 and D181 visits. For other lab related blood sample deviations, code 99 will be used which will not lead to any exclusion from the PPS.

The number of participants with important protocol deviations will be summarized by study group across time points separately (ie Day 29, 91 and Day 181. Important protocol deviations will be listed with date of occurrence, deviation description, and analysis set, including time point for PPS) from which participant is excluded. Important protocol deviation summary will be based on the Enrolled Set.

The important PDs will be reported in the Clinical Study Report (CSR). The important PDs leading to elimination from the PPS will be summarized by study group for the ES and the important PDs leading to elimination from the ES will be summarized across groups (ie pooled groups) for the Enrolled Set.

- Data will be reviewed prior to freezing the database to ensure all important deviations (where possible without knowing the study intervention details) are captured and categorised in the protocol deviations dataset.
- This dataset will be the basis for the summaries of important protocol deviations.

**Table 3      Intervals between study visits**

Interval	Planned visit interval	Allowed interval range
Visit 1 (Day 1)→Phone call / CCI (Day 8)	7 days	7±1
Visit 1 (Day 1)→Visit 2 (Day 29)	28 days	28±3
Visit 1 (Day 1)→Visit 3 (Day 91)	90 days	90±7
Visit 1 (Day 1)→Visit 4 (Day 181)	180 days	180±7

If the study intervention date is different from the ICF signature date, the study intervention date needs to be taken as a reference for calculating intervals relative to subsequent visits.

Interval is computed as the difference between 2 dates.

#### 6.1.4.      Prior and Concomitant Medications

Concomitant medications are defined as any medications and vaccines (other than study intervention) taken after the study intervention administration. Any medication or vaccine (other than study intervention) started prior to the study intervention administration and continued after the study intervention administration will be considered a concomitant medication.

Concomitant medications/vaccinations will be coded using both the GSK Drug and WHO Drug dictionaries and will be listed and summarized descriptively (any medication, any antipyretic, and any antipyretic taken prophylactically, respectively) by study group using the ES.

The antipyretic classification is derived from the following ATC code

ATC Code
A03D, A03DA, A03DB, A03DC, A03EA
M01, M01A, M01AA, M01AC, M01AE, M01AG, M01AB, M01AH, M01AX, M03B, M03BA, M03BB, M03BB, M03BC, M03BX
N02BG, N02AC, N02AG, N02AX, N02B, N02BA, N02BB, N02BE
R05, R05D, R05X

The percentage of participants using concomitant medication (any medication, any antipyretic and any antipyretic taken prophylactically, respectively) during the 28-day follow up period (i.e., Day 1-Day 28 post-dose) will be summarized by group.

## 6.2. Appendix 2: Data Derivations Rule

### 6.2.1. Data derivation

This section includes complementary derivation rules.

#### 6.2.1.1. Weight

Weight will be presented in kilograms. Weights reported in pounds will be converted as follows:

$$\text{Weight in kilograms} = \text{Weight in pounds} / 2.2$$

#### 6.2.1.2. Height

Height will be presented in centimeters. Heights reported in feet and inches will be converted as follows:

$$\text{Height in centimeters} = \text{Height in inches} \times 2.54$$

#### 6.2.1.3. Body Mass Index (BMI)

BMI will be calculated as follows:

$$\text{BMI} = (\text{Weight in kilograms}) / (\text{Height in meters})^2$$

#### 6.2.1.4. Temperature

Temperatures will be presented in degrees Celsius (°C). Temperatures reported in degrees Fahrenheit (°F) will be converted as follows:

$$\text{Temperature (Celsius)} = ((\text{Temperature (Fahrenheit)} - 32) \times 5)/9$$

#### 6.2.1.5. Numerical serology results

Numerical serology results will be derived from the content of IS.ISORRES in the SDTM dataset. For assays with a specific cut-off, with the exclusion of **CCI** data, the following derivation rules apply:

**Table 4 Numerical serology results**

IS.ISORRES	Derived value
“NEG”, “-”, or “(-)”	cut-off/2
“POS”, “+”, or “(+)”	cut-off
“< value” and value is <= assay cut-off	cut-off/2
“< value” and value is > assay cut-off	value
“> value” and value is < assay cut-off	cut-off/2
“> value” and value is >= assay cut-off	value
“value” and value is < cut-off	cut-off/2
“value” and value is >= cut-off	value
All other cases	missing

#### **6.2.1.6. Geometric Mean Titres (GMTs) and Concentrations (GMCs)**

Geometric Mean Titre (GMT) or Concentration (GMC) calculations are performed by taking the inverse logarithm of the mean of the log titre or concentration transformations. Non quantifiable titres or concentrations will be converted as described in Section 6.2.1.5 for the purpose of GMT/GMC calculation. Cut-off values are defined by the laboratory before the analysis.

#### **6.2.1.7. Onset Day**

The onset day for an event (e.g., AE, concomitant medication/vaccination) is the number of days between the study dose administration and the start date of the event. This is 1 for an event occurring on the same day as a study dose when the timing of vaccination is prior to the onset time of the AE.

#### **6.2.1.8. Study Day**

Study day will be calculated as follows:

- Study day prior to dosing will be calculated as: date of assessment – date of the study intervention administration
- Study day on or after the date of the dosing will be calculated as: date of assessment – date of the study intervention administration + 1.

#### **6.2.1.9. Solicited and Unsolicited AEs**

For clinicaltrials.gov and EudraCT posting purposes, the number and percentage of participants reporting any solicited and unsolicited adverse events excluding SAE will be summarized according to MedDRA PTs together with the number of events. A solicited AE starting within the solicited period (day 1-7) will be counted as one

event. Unsolicited AE, excluding prolonged solicited AE, with the same PT and start date will be counted as one event. Solicited AEs will be mapped to MedDRA as follows:

**Table 5      Mapping of solicited events to MedDRA**

Solicited event	Lower level term code	Corresponding Lower level term decode
Pain	10022086	Injection site pain
Erythema	10022061	Injection site erythema
Swelling	10053425	Injection site swelling
Lymphadenopathy	10025197	Lymphadenopathy
Fever	10016558	Fever
Headache	10019211	Headache
Fatigue	10016256	Fatigue
Myalgia	10028411	Myalgia
Arthralgia	10003239	Arthralgia
Chills	10008531	Chills

#### **6.2.1.10. Duration of Events**

The duration of an event with a start and end date will be the difference between the start and end date plus 1 day, i.e., an event that starts on 03MAR2018 and ends on 12MAR2018 has a duration of 10 days.

For any grade, duration of solicited AE is defined as Stop date – Start date + 1, with Start date defined as the first day with the symptom at Grade  $\geq 0$  within the 7-day solicitation period and Stop date defined as the last day with the symptom (i.e., Grade  $> 0$ ) in or beyond the solicited period. For solicited AE continuing beyond Day 7, stop date will be the last day with the symptom . .

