**Table 16 Intensity scales for solicited events**

Event	Intensity grade	Parameter
Pain at administration site	0	None
	1	Mild: Any pain neither interfering with nor preventing normal everyday activities
	2	Moderate: Painful when limb is moved and interferes with everyday activities
	3	Severe: Significant pain at rest. Prevents normal everyday activities
Redness at administration site	0	<2.5 cm
	1	2.5 – 5 cm
	2	5.1 – 10 cm
	3	>10 cm
Swelling at administration site	0	<2.5 cm
	1	2.5 – 5 cm
	2	5.1 – 10 cm
	3	>10 cm
Lymphadenopathy*	0	None
	1	Mild: No interference with activity
	2	Moderate: Some interference with daily activity or requires repeated use of non-narcotic pain reliever
	3	Severe: Prevents daily activity or requires use of narcotic pain reliever
Temperature**	0	<38.0°C or <100.4°F
	1	38.0 – 38.4°C or 100.4 – 101.1°F
	2	38.5 – 38.9°C or 101.2 – 102.0°F
	3	>38.9°C or >102.0°F
Headache	0	Normal
	1	Mild: Headache that is easily tolerated
	2	Moderate: Headache that interferes with normal activity
	3	Severe: Headache that prevents normal activity
Fatigue	0	Normal
	1	Mild: Fatigue that is easily tolerated
	2	Moderate: Fatigue that interferes with normal activity
	3	Severe: Fatigue that prevents normal activity
Myalgia	0	Normal
	1	Mild: No interference with daily activity
	2	Moderate: Interferes with daily activity
	3	Severe: Prevents daily activity
Arthralgia	0	Normal
	1	Mild: No interference with daily activity
	2	Moderate: Interferes with daily activity
	3	Severe: Prevents daily activity

Event	Intensity grade	Parameter
Chills	0	None
	1	Mild sensation of cold; shivering; chattering of teeth
	2	Moderate tremor of the entire body; narcotics indicated
	3	Severe or prolonged, not responsive to narcotics

\* Defined as localized axillary, cervical or supraclavicular swelling or tenderness ipsilateral to the vaccination arm.

\*\* Refer to Section 10.3.3 for the preferred location for temperature measurement.

The investigator will make an assessment of intensity for each AE/AESI/SAE reported during the study and assign it to one of the following categories:

- Mild:  
A type of AE that is usually transient and may require only minimal treatment or therapeutic intervention. The event does not generally interfere with usual activities of daily living.
- Moderate:  

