**CCI**

## Objectives and endpoints for Part B

Primary Safety Objective	Primary Safety Endpoints (population summary)

 
To evaluate the safety and reactogenicity of three CV0801 booster vaccine manufacturing specifications
 
	
 
Solicited events:
 
Occurrence of solicited administration site and systemic AEs within 7 days (i.e., from Day 1 to Day 7 included) of study intervention administration (percentage of participants)
 
Unsolicited events:
 
Occurrence of unsolicited AEs within 28 days (i.e., from Day 1 to Day 28 included) of study intervention administration (percentage of participants)
 
SAEs, AESIs and MAAEs:
 
Occurrence of MAAEs, SAEs and AESIs from Day 1 through the end of the study (approximately 180 days after the study intervention administration), each summarized separately (percentage of participants)
 

Primary Immunogenicity Objective	Primary Immunogenicity Endpoint (population summary)

 
To evaluate the immunogenicity of three CV0801 booster vaccine manufacturing specifications
 
	
 
Serum neutralization titers against pseudovirus bearing specific CCI [REDACTED] spike protein at Day 29 (GMT)
 

AE: adverse event; AESI: adverse events of special interest; GMT: geometric mean titer; MAAE: medically attended adverse event; SAE: serious adverse event

Complementary information on estimands can be found in Section 3.

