##### **4.2.1.1. Solicited AEs**

All solicited events must be recorded into the eDiary by the participant during the first 7 days following administration of the dose of study intervention (Day 1 to Day 7 included), irrespective of occurrence or intensity. Solicited events ongoing after Day 7 will be recorded in the eCRF and followed-up until the event has resolved, subsided, stabilized, disappeared, or until the event is otherwise explained, the participant is lost to follow up, or study is completed. If the collection of solicited AEs was not possible for any reasons via the eDiary and solicited AEs were reported to the investigator by the participant, then it would be possible for them to be reported directly to the site staff and submitted (e.g., via the eCRF).

The following administration site events will be solicited:

- a. Pain
- b. Redness
- c. Swelling
- d. Lymphadenopathy, defined as localized axillary, cervical or supraclavicular swelling or tenderness ipsilateral to the injection arm

The following systemic events will be solicited:

- e. Fever
- f. Chills
- g. Headache
- h. Fatigue

- i. Myalgia
- j. Arthralgia

Note: Participants will be instructed to measure and record the axillary temperature in the evening. If additional temperature measurements are taken at other times of the day, participants will be instructed to record the highest temperature in the eDiary.

Grading or actual temperature/redness and swelling will be captured in the eDiary as per a modified grading of symptoms based on the FDA toxicity grading guidance for industry [FDA, 2007] with Grades 3 and 4 combined and swelling evaluated using the actual measurement only (refer to Section 6.2.2.2). When solicited AE data entered by the participant are missing or incorrect, data collected by study investigator/staff will be used in the summaries if available.

The percentage of participants reporting each individual solicited administration site event (any grade, Grade 1, Grade 2, Grade 3, any grade ongoing at day 7 and medically attended events) and solicited systemic event (any grade, Grade 1, Grade 2, Grade 3, any grade ongoing at day 7 and medically attended events) within the 7-day follow up period (i.e., Day 1-Day 7 post-dosing) will be tabulated for each group.

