The duration of solicited AEs of any grade (see Section 6.2.1.10) will be summarized. The start date is the first day during the 7-day solicitation period with the symptom at grade > 0 while the stop date is the last day with the symptom at grade > 0 in or beyond the solicited period. In addition, the duration for specific grade(s) for each symptom defined as the number of days in the reporting period with grade above or equal to specific grade will be summarized.

Prolonged solicited AEs that continue beyond Day 7 or Day 28 will be identified using a flag in listing of AEs.

The percentage of eDiary days completed in the solicited period will be summarized by group. A day is considered completed in the eDiary if it was entered by the participant or the investigator. The percentage of completed days will be calculated as follows:

$$\text{SumSymp}/(7*\text{NumSymp}*\text{ExpSubj})$$

SumSymp is the sum of the total number of days completed for a specific symptom across all symptoms and exposed subjects. NumSymp is the number of symptoms and ExpSubj is the number of exposed subjects.

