#### 6.2.2.2. Daily Recording of Solicited Events

For studies **using electronic diaries** for the collection of solicited events, a solicited event will be considered present only when a daily recording of Grade 1 or more is present. To determine the grading, the following rule will be used:

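### SAP 6.2.1.10 starts any-grade solicited-AE duration at Grade ≥ 0, while SAP 4.2.1.1 starts it at Grade > 0; followed literally, the appendix rule overstates duration by 0 to 6 days

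*SAP*

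**What the plan says.** The SAP defines the any-grade duration of a solicited AE twice.

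- **SAP 4.2.1.1 (Solicited AEs)** announces the summary, points to 6.2.1.10, and then gives its own rule: "The start date is the first day during the 7-day solicitation period with the symptom at grade > 0". The stop date is the last day above Grade 0, in or beyond the solicited period.
- **SAP 6.2.1.10 (Duration of Events)** sets duration at stop date minus start date plus 1, with "Start date defined as the first day with the symptom at Grade"; the condition that follows those words is ≥ 0, within the 7-day solicitation period. The same sentence continues with "Stop date defined as the last day with the symptom (i.e., Grade", and there the condition is > 0.

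Three other statements bear on which condition is meant and on what the difference does:

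- SAP 6.2.2.2 (Daily Recording of Solicited Events): "a solicited event will be considered present only when a daily recording of Grade 1 or more is present".
- Protocol Table 16 lists Grade 0 for every solicited event. It stands for none or normal, for redness or swelling below 2.5 cm, and for a temperature of "<38.0°C or <100.4°F".
- SAP 4.2.1.1 requires eDiary recording for "Day 1 to Day 7 included), irrespective of occurrence or intensity", so days without symptoms are recorded too.

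**The concern.** The two sections define one quantity, and the main text sends the reader to the section with the different start condition. Because Grade 0 is a real value and symptom-free days are recorded, a condition of Grade ≥ 0 is met by the first diary day that carries any entry. A program written from the derivation appendix would count symptom-free days before onset as part of the event. With a complete diary the result no longer depends on onset at all: it is simply the day number of the last symptomatic day.

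At stake is one planned descriptive reactogenicity summary, in both Part A and Part B. The excess grows with later onset, so if the groups differed in time to onset, the distortion would differ between them as well. The outputs could also disagree with each other. SAP 4.2.1.1 plans a grade-specific duration in which "the number of days in the reporting period with grade above or equal to specific grade will be summarized". For a one-day Grade 1 event starting on Day 3, that count at Grade 1 or above is 1, while the any-grade duration read literally is 3.

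**Working it through.** **Inputs**

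- Duration = stop − start + 1 (SAP 6.2.1.10).
- Solicitation period: Day 1 to Day 7 (SAP 4.2.1.1; protocol 8.4.1).
- *f* = first diary day with a recorded grade; *o* = first day with Grade > 0; *s* = last day with Grade > 0.

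**The plan's own example.** SAP 6.2.1.10 gives 10 days for an event from 03MAR2018 to 12MAR2018. The formula returns 12 − 3 + 1 = 10, so the basic formula is sound and only the start date is in question.

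**The two rules**

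- SAP 4.2.1.1 (start at Grade > 0): *s* − *o* + 1.
- SAP 6.2.1.10 read literally (start at Grade ≥ 0): *s* − *f* + 1.
- Excess: (*s* − *f* + 1) − (*s* − *o* + 1) = *o* − *f*.

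**Size with a complete diary (*f* = 1).** The excess is *o* − 1:

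| Onset day | 1 | 2 | 3 | 4 | 5 | 6 | 7 |
|---|---|---|---|---|---|---|---|
| Excess (days) | 0 | 1 | 2 | 3 | 4 | 5 | 6 |

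**Examples**

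- Grades 0, 0, 1, 0, 0, 0, 0: *o* = *s* = 3. SAP 4.2.1.1 gives 3 − 3 + 1 = 1 day; the literal rule gives 3 − 1 + 1 = 3 days. If Day 1 was not recorded (*f* = 2), the literal rule gives 3 − 2 + 1 = 2 days.
- Last symptom on Day 4, complete diary: the literal rule gives 4 days whether the event began on Day 1 (true duration 4) or on Day 4 (true duration 1).
- Onset Day 4, last symptom Day 7: 7 − 4 + 1 = 4 days against 7.
- Onset and end both on Day 7: 1 day against 7, the largest excess.

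**Exhaustive check.** Each day was classed as symptom-free or symptomatic, and every 7-day pattern with at least one symptomatic day was listed: 2^7 − 1 = 127 patterns. With a third state for a missing day there are 3^7 − 2^7 = 2187 − 128 = 2,059. In every pattern the excess equalled *o* − *f*, with a range of 0 to 6 days. These counts only verify the formula; they say nothing about how often each pattern would occur.

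**What is not touched.** A participant with no day above Grade 0 has no stop date under either rule, so no event or duration is created. The primary safety endpoint, "Occurrence of solicited administration site and systemic AEs within 7 days", does not use the start date of an event's duration. Nor do the maximum grade or the grade-specific day counts.

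**The case against.** The strongest reply is that ≥ 0 is an obvious slip that the SAP itself resolves. The rule speaks of a day on which the symptom is present, the stop rule in the same sentence explains that as Grade > 0, and 6.2.2.2 recognises an event only from Grade 1. The appendix describes its rules as complementary, so the fully stated rule in 4.2.1.1 could be taken to prevail. This stands as evidence of intent: > 0 is almost certainly meant. It does not remove the conflict, because 4.2.1.1 refers the reader to 6.2.1.10 for this derivation and nothing states which section governs.

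Four further points narrow the concern without defeating it:

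- SAP Tables 6 and 7 list only Grades 1 to 3, so the presence of Grade 0 in the analysis data rests on protocol Table 16 and on the condition > 0 in 4.2.1.1, which presupposes a Grade 0.
- Solicited AEs may be reported to site staff and entered in the eCRF when the eDiary could not be used. The documents do not say that symptom-free days are recorded by that route, so the formula may not apply there.
- The range of 0 to 6 days is an envelope set by the 7-day window, not an expected bias.
- Duration is not a listed endpoint in either part, and no stated decision rule uses it. This limits the importance of the point.

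A misread symbol in the converted text is possible but unlikely, since the > in the same sentence came through as a different symbol.

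**Conclusion.** The concern holds. SAP 6.2.1.10 and 4.2.1.1 give different start conditions for the same summary, and the one in 6.2.1.10 produces wrong durations if it is programmed as written. The excess for an event is its onset day minus the first recorded diary day. It is zero when the symptom is present on the first recorded day and 6 days at most.

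This rests on two assumptions: symptom-free diary days carry Grade 0 in the analysis data, and the program follows 6.2.1.10 literally. If it follows 4.2.1.1, there is no error. The average overstatement cannot be given, because the documents contain no distribution of onset days. The effect is confined to the descriptive any-grade duration summary, so this should be corrected but does not threaten any primary conclusion.

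**What to change.** In SAP 6.2.1.10, change the start condition from Grade ≥ 0 to Grade > 0, so that it agrees with 4.2.1.1, with 6.2.2.2 and with its own stop rule. Then run the programmed derivation on a test record with daily grades 0, 0, 1, 0, 0, 0, 0: it must return 1 day, and a result of 3 shows that the literal rule was coded.

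The cost is one symbol in the SAP and one programming check. No data collection, endpoint or other analysis changes.
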